PROTOCOL TITLE: “Evaluating the efficacy of micro-fragmented adipose tissue and intra-articular corticosteroid injections for symptomatic knee osteoarthritis: a randomized, placebo controlled study”

requirements within 15 months of enrollment. We anticipate needing two months for data analysis.

- *The facilities available for the research include: University of New Mexico Hospital including clinics and operating facilities for patient recruitment, the facilities made available for the Orthopedic Department, the CTSC facilities for participant procedures and follow-up, and the UNM IDS Pharmacy for drug storage and handling.*
- *Subjects that may desire further medical attention may request to be removed from participation in the study and can then choose to pursue further care with the physician of their choice.*
- *All persons assisting with the study will be trained on the protocol, consent process, and data collection by [name], the principal investigator, prior to participating in the study.*
- *We will also be utilizing the CTSC research facility and resources for conducting this study, including their statistical department, rooms and facilities, and their study coordinators to help gather survey data.*

10. Prior Approvals

10.1. We will be awaiting funding approval and IRB approval prior to conducting the research. We have already received departmental approval.

10.2. Departmental Review Form.

10.3. Not applicable. No x-rays are required during participation in the study. Patients who qualify for the study will have obtained standard of care x-rays prior to enrollment in the study as part of their provider's evaluation.

10.4. Drug attachment.

11. Multi-Site Research

11.1. Not applicable. This study will be conducted at the University of New Mexico Hospital and CTSC and will not include any other sites

11.2. Not applicable. This study will be conducted at the University of New Mexico Hospital and CTSC and will not include any other sites.

11.3. Not applicable. The treatments used in this study are FDA approved and being used in the manner intended.

12. Study Procedures

12.1. In chronological order, all research procedures and interventions being performed and when they are performed.

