- 14.4. *The existing literature has been reviewed regarding Lipogems®. A board certified plastic surgeon was consulted regarding adverse effects of lipoaspiration procedures and the adverse risks are detailed in this protocol and the consent form.*
- 14.5. *N/A. Safety data is not collected in this study.*
- 14.6. *The research will be suspended and/or terminated if there is an unexpected serious adverse event that requires further investigation.*

15. Withdrawal of Subjects

- 15.1. *We do not anticipate any medical reasons to withdraw subjects from the study without their consent. If participants are not adherent and miss follow-up appointments, refuse to be scheduled, or do not respond to scheduling requests, they will be withdrawn from the study.*
- 15.2. *Participants may withdraw at their request and continue to seek standard of care treatments with the physician of their choice. No labs/tapering of meds/or physical exams are necessary to withdraw.*
- 15.3. *Partial withdrawal will be permitted if a patient desires to continue participating in data collection but no longer wishes to be seen for follow-up. The questionnaires would be completed online only. All previously collected data will still be used for research purposes unless the patient explicitly asks for data to be excluded.*
- 15.4. *If a patient withdraws, all previously collected data will still be used for statistical analysis unless the participant explicitly asks for their previous data to be excluded from further consideration. Describe the disposition of existing data/specimens when a subject withdraws.*
- 15.5. *If a patient requests to be withdrawn, [name], the principal investigator, must be made aware. If the patient requested that their data be destroyed and not used for analysis, then the data will be properly destroyed. Otherwise, data that was collected prior to withdrawal from the study may be used for analysis.*

16. Data Management/Confidentiality

- 16.1. *Members of the research team will be permitted to access the participants' medical records through PowerChart to confirm participant eligibility and document procedures and follow-up visits. PHI will be reviewed as part of the normal screening process in clinic.*
- 16.2. *Members of the research team will have access to direct identifiers only as necessary to confirm participant eligibility and document procedures and follow-up visits.*

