PROTOCOL TITLE: “Evaluating the efficacy of micro-fragmented adipose tissue and intra-articular corticosteroid injections for symptomatic knee osteoarthritis: a randomized, placebo controlled study”

23. Compensation

23.1. Participants will be compensated for their participation by receiving a reloadable gift card. They will receive \$25 at each in person follow-up visit. They will be compensated \$10 each time they complete the online surveys. Each participant will be asked to return for 2 follow-up visits (6 weeks and 6 months, post-procedure) and complete the online surveys 3 times for a total of \$80 compensation for participating.

24. Compensation for Research-Related Injury

24.1. If a patient elects to withdraw from the study, i.e. for further treatment/care elsewhere, the patient may withdraw. We do not anticipate any more risk than standard of care would provide to the patient. The patient can elect to pursue standard of care treatments as determined by the patient and their physician.

24.2. Study subjects will be monitored at follow-up appointments. If a subject is unhappy with their treatment outcome throughout the course of the study, they may elect to withdraw from the study and pursue their own care with the physician of their choice.

25. Consent Process

25.1. Participants must provide research staff with informed consent prior to enrolling in the study.

25.1.1. Consent may be obtained by [name], [name], [name], [name], and [name] and any other approved investigators listed in the Click IRB record. The process for obtaining informed consent and consent form will be reviewed with each member of the research staff responsible for obtaining consent by [name].

25.1.2. Consent will take place at the various clinics/hospitals associated with the University of New Mexico Hospital and the Orthopedics Department. Consent will only be obtained in a private patient room. No one besides the patient and study staff will be in the room at the time of consent. If the patient requests a family member or friend be in the room during the time of their appointment/consent, the patient’s request will be honored.

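### Participants who want other care or are unhappy with the result are pointed to withdrawal rather than to continued questionnaires, and no named instrument records other knee procedures: a modest, cheaply reduced risk to the late Lipogems comparisons

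*Combined protocol and SAP*

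**What the plan says.** Several sections name withdrawal as the option for someone who wants more care or is dissatisfied:

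- Section 9.3: "Subjects that may desire further medical attention may request to be removed from participation in the study". Further care is mentioned after removal.
- Section 24.1: "If a patient elects to withdraw from the study, i.e. for further treatment/care elsewhere, the patient may withdraw".
- Section 24.2: "If a subject is unhappy with their treatment outcome throughout the course of the study, they may elect to withdraw from the study".
- Section 15.2 also mentions withdrawal and standard care together.

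Section 15.1 adds a rule for non-attenders: "If participants are not adherent and miss follow-up appointments, refuse to be scheduled, or do not respond to scheduling requests, they will be withdrawn". After full withdrawal, 15.4 and 15.5 provide only for data already in hand: "If a patient withdraws, all previously collected data will still be used for statistical analysis unless the participant explicitly asks".

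Other text points the other way. The last sentence of 24.1 reads "The patient can elect to pursue standard of care treatments as determined by the patient and their physician", with no condition of exit. Section 15.3 says "Partial withdrawal will be permitted if a patient desires to continue participating in data collection but no longer wishes to be seen for follow-up"; such a person then answers by online survey alone.

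The follow-up instruments named in 12.1 (items 3 and 5) are WOMAC, VAS, KOOS and a log of any medications taken. Section 16.1 gives the team access to "medical records through PowerChart to confirm participant eligibility and document procedures and follow-up visits". Section 5.3 mentions drop-out only as a possible loss of power.

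**The concern.** Pain is a main outcome, and dissatisfaction with the result is one of the stated occasions for leaving. Drop-out can therefore depend on the very score that goes missing. Placebo and corticosteroid participants are blinded and Lipogems participants are not (3.2), so the rate of leaving, or the reasons for it, may differ in comparisons with Lipogems.

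The mixed model of 13.1 uses all recorded scores and so accounts for the part of drop-out that those scores predict. It cannot account for a worsening after the last completed survey, and the last two intervals are 3 and 6 months long.

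Co-treatment is the second issue. If someone has another injection or an operation and stays in the study, nothing described in the plan reliably records it. Scores and treatment dates that were never collected cannot be recovered at analysis.

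**Working it through.** **What the sections provide for a participant treated elsewhere**

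| Question | Text | Answer |
|---|---|---|
| Must they leave? | 9.3, 15.2, 24.1, 24.2 | No; the wording is permissive, but leaving is the option named |
| Does any section say they may be treated and stay in follow-up? | 24.1 last sentence; 15.3 | Not expressly; 24.1 allows care without mentioning data, and 15.3 allows data without mentioning care |
| Can they be withdrawn without asking? | 15.1 | Yes, if they miss visits or do not respond |
| Is another injection, procedure or surgery recorded? | 12.1; 16.1, 16.3 | An injected drug possibly, in the log; in-system procedures possibly, in the chart; no systematic capture is described |

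**The plan's own figure (context only).** With a 15-point difference, SD 20, 5% error and 80% power, n = 2 × [SD × (z_alpha + z_power) / difference]². One-sided: 2 × [20 × (1.645 + 0.842) / 15]² = 21.98, which is the plan's 22 per group. Two-sided it is 27.9, so 28. The point here does not depend on this.

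**Size of the possible bias (illustration).** Inputs from 5.3: SD 20 (35 as the plan's conservative value), true benefit 15, n = 25 per arm. Assumed, because the documents give no rates: the worst 20% of placebo and the worst 10% of Lipogems miss the 1-year score; correlation between visits 0.5 or 0.7, either equal or decaying from visit to visit. The mixed model is approximated by regression on all earlier scores within each arm, with 400,000 simulated participants per arm and Monte Carlo error of about 0.1.

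Standard error of a single-visit difference = SD × √(2/25) = 5.66 at SD 20 and 9.90 at SD 35.

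Upper reference, using completers only: each arm's mean shifts by SD × φ(z)/(1 − p). This is 7.0 for p = 0.20 and 3.9 for p = 0.10, a difference of 3.1 points.

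Estimated minus true benefit at 1 year, SD 20 (correlation 0.5 / 0.7):

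| What drives leaving | Equal correlation | Decaying correlation |
|---|---|---|
| Entirely the unseen score | −2.4 / −1.7 | −2.7 / −2.2 |
| Correlates 0.5 with the unseen score | −0.9 / −0.7 | −1.2 / −0.8 |
| Last recorded score only | 0 / 0 | 0 / 0 |

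Across 6 months, 1 year and repeated runs the ranges are 1.7 to 2.8, 0.6 to 1.3, and about 0. In standard errors: 1.7/5.66 = 0.30 to 2.8/5.66 = 0.49; 0.6/5.66 = 0.11 to 1.3/5.66 = 0.23; and 0.

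Variations:

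- Rates reversed (placebo 10%, Lipogems 20%): the same sizes with opposite sign, +1.7 to +2.7 and +0.7 to +1.2.
- Rates equal (20% in both arms): within 0.2 of zero.
- SD 35: 3.0 to 4.8, 1.0 to 2.2, and about 0, against a standard error of 9.90.

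**Whole-follow-up contrast.** Take an equal-weight mean of five visits (an assumption). If only the 1-year visit is affected, the worst case is 1.7/5 = 0.3 to 2.8/5 = 0.6 points. If 6 months is equally affected, it is 0.7 to 1.1 points. The standard error is 5.66 × √[(1 + 4r)/5] = 4.4 at r = 0.5 and 4.9 at r = 0.7. The bias is then about 0.1 standard error, or at most 1.1/4.4, about 0.3.

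**Power, single-visit two-sided t test, n = 25, SD 20.** A difference of 15 gives 74%. With the worst-case shift, 15 − 1.7 = 13.3 gives 64% and 15 − 2.8 = 12.2 gives 56%.

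**The case against.** Sections 9.3 and 24 deal with resources and injury compensation, and they say only that a participant may leave. The operative rules are in section 15: 15.1 does not list other treatment as a ground for withdrawal, and nothing in 15.3 excludes a person treated elsewhere. Oral medication is left alone and logged at every time point. Retention is also supported. Placebo participants are offered a corticosteroid injection only after the 1-year questionnaire (12.1 item 7, 27.1, 28.2), and follow-up visits and online surveys are paid (23.1). The 20%/10% split comes from no document, and 13.1 compares whole trajectories as well as single visits.

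Most of this stands, and it rules out three stronger readings that a reader might infer. First, the plan does not force out people who seek other treatment, and their later scores are not necessarily lost. Second, it cannot be said that other treatments go unrecorded: the log may show an injected drug, the chart may show in-system procedures, and the forms themselves are not available. Third, the bias cannot be said to run against Lipogems, or in any known direction; the sign follows from which arm is assumed to lose more.

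What remains is that the route for staying is not directed to the people most likely to leave because of their outcome, that 15.1 can remove them, and that no named item asks about other knee procedures.

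**Conclusion.** The point holds as a cheap improvement of modest size. Bias at the late visits needs two things together: leaving that depends on pain not yet recorded, and rates that differ between Lipogems and its comparator. Under the assumed 20% and 10%, it is at most about half a standard error at one visit and about 0.1 to 0.3 for an average over follow-up. It is about zero if either condition fails. Because the rates are assumptions, these figures show a range, not a likely value, and the direction is unknown. The corticosteroid-placebo comparison is less exposed, since both of those arms are blinded. Nothing here overturns the trial.

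**What to change.** 1. In 9.3, 24.1 and 24.2, with matching words in 15.1 to 15.3, state that a participant who wants or receives other treatment for the knee may have it and remain in the study. Before anyone is withdrawn, offer the scheduled questionnaires to 1 year, online (15.3) or by phone (12.1 item 5). Full withdrawal stays available at any time. The continuation question in 25.1.5 is a natural moment for the offer.

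2. Unless the form already has it, add one line to the log at each contact: any other knee injection, procedure or surgery since the last survey, with type, knee and date.

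The cost is a few sentences and one log line, and clinical care does not change. The consent form was not available to this review and needs a change only if it says otherwise.

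There is a downside. Scores after later treatment enter the assigned-arm contrast, which may shrink. If a fraction f of placebo participants gained the full 15 points elsewhere, the contrast would be 15 × (1 − f): 13.5, 12.0 or 10.5 for f = 10%, 20% or 30%. Single-visit power would fall from 74% to 65%, 55% or 44%. The change does not promise a larger effect. Its gain is that the late scores exist and switching is visible, whichever question the investigators choose to answer.
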